3.2 Secondary Objectives

- 1) To examine the association of baseline demographic characteristics and HIV incidence and prevalence in a household-based representative sample of men and women before and after completion of the MC ASI.
- 2) To determine the prevalence of circumcision among a household-based representative sample of men before and after completion of the MC ASI.
- 3) To estimate HIV prevalence rates among men and women in a household-based representative sample of men and women before and after completion of the MC ASI.
- 4a) To describe sexual risk behavior and exposure to sexual risk reduction campaigns in a household-based representative sample of men and women before and after completion of the MC ASI.
- 4b) To assess sexual risk behaviors in a highest risk age subset of the household-based, nationally representative sample, men ages 25-34, for an additional 6-18 months after the MC ASI completion.
- 4c) To assess sexual risk behaviors in a highest risk age subset of the household-based, nationally representative sample, women ages 18-24, for an additional 6-18 months after the MC ASI completion.
- 5) To describe the proportion of HIV-infected men and women in a household-based representative sample with undetectable viral loads before and after completion of the MC ASI.
- 6) To measure the proportion of HIV-infected men and women in a household-based representative sample who report engagement in HIV care and ART use before and after completion of the MC ASI.

- 7) To estimate the annual number of HIV infections averted among men due to MC.
- 8) To describe the concurrent CD4 count and viral load distributions in a nationally representative sample of HIV-infected men and women ages 18-49, in the context of ART use.
- 9) To estimate the proportion of HIV-infected men and women ages 18-49 who have a CD4 count <350 cells/mm³ and who report no current ART use.

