4.2 How study design meets objectives and addresses research questions

The study design incorporates two different strategies for measuring the change in seroincidence. To measure the population effect of the MC ASI campaign on HIV infection in Swaziland, we plan two independent household based samples, one prior to the campaign, one 12 months after the completion of the campaign. Each gives an

independent population “snapshot” of the current rates of infection. The second strategy enrolls a cohort of men and women in the ages at highest risk prior to the MC ASI and measures that seroincidence in this group for an additional 6-18 months after the campaign’s completion. There are several reasons for this hybrid approach. Two sequential short term cohorts provide two similar ‘snapshots’ of HIV incidence before and after the ASI campaign and coinciding with scale-up of other prevention programs. These two cohorts are representative of the national population and the HIV seroincidence estimates before and after ASI are therefore likely to represent actual changes in the epidemic. The use of a more traditional longitudinal cohort is conceptually familiar from randomized placebo controlled clinical trials; here it is used to follow HIV incidence among young adults in the highest incidence age groups over an additional 6-18 month period.

The comparison of HIV incidence rates between circumcised and uncircumcised men offers insight into the role played by MC in reducing HIV infection in the cohort and in the general population, if observed.

Blood specimens from persons identified as HIV-infected *during pre-cohort surveys* (A1 and A2) will be collected to measure viral load. These data will be used to determine the proportion of HIV infected persons with undetectable viral load in the community. The proportion of undetectable viral load at the baseline pre-cohort survey will be compared to the post-MC ASI pre-cohort survey to explore the potential effect of scale up of the ART program and viral suppression on reduced HIV incidence in the general population, if observed.

Blood specimens to measure CD4 count will be collected using a multistage clustered random sample of persons who were identified as HIV-seropositive at the pre-cohort survey for Cohort A1 (T1). These data will be used to estimate the CD4 count distribution, viral load distribution, and self-reported ART use among HIV-infected individuals at the population-level.

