6.5 Study Assessments

6.5.1 Laboratory Assessments

HIV status: At all study visits HIV status will be determined using a serial algorithm for rapid tests approved by the Swaziland National Reference Laboratory. (Appendix A). HIV rapid test result data will be recorded on the HIV Test Results Case Report Form. (Appendix G)

Viral load measurement: Men and women who test HIV-positive via an HIV rapid test during the pre-cohort surveys will have blood specimens tested for viral load. Men and women who participate in Cross Sectional Cohort C and who agree to have their blood specimen stored for future testing will have their specimens tested for viral load.

CD4 count: Blood specimens from participants in Cross-Sectional Cohort C will be analyzed for CD4 count.

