The household sample of 14,884 and 15,758 in pre- and post- MC-ASI is expected to yield an enrolled cohort of 7106 women and 7,524 in the pre- and post-MC ASI cohorts respectively. (See Table 3)

Number of effective women-years accumulated-

The number of effective women years accumulated from the household sample of 14,884 and 15,758 in pre- and post- MS-ASI is shown in Table 3. The derivation of each of the adjustment factors is as follows:

- Design Effect: Design effect for HIV in women ages 15-49 of 1.25, and the DEFT of 1.32, are both based on the 2006-07 DHS.
- Household adjustment
 - 13% will be vacant/non-contactable, 5% will refuse participation at the household level. Adjustment factor = $1/0.87 \times 0.95 = 1.21$
- Household individual adjustment
 - Women: 105% will have female residents within the eligible age range, 65% will be HIV uninfected, 99% will agree to cohort enrollment, 90% will be contactable, 95% will agree to pre-cohort survey. Adjustment factor = $1/(1.05 \times 0.65 \times 0.99 \times 0.90 \times 0.95) = 1.73$
- Loss to follow-up

Women: 92% and 88% of women will complete follow-up in the 6 and 12 month cohorts, respectively (accounting for loss-to-follow-up, interview/HIV test refusal, data loss, and specimen loss totaling 8% and 12%, respectively). Adjustment factor = $1/0.92 = 1.09$ and $1/0.88 = 1.14$ respectively.

Table 3: Number of enrolled female participants, given sample of 14,884 and 15,758 households in the pre- and post-MC ASI cohort.

Effective number person years	Design effect	Loss to follow-up adjustment	Number Females enrolled	Female household adjustment	Number of households participating	Household adjustment	Number of households sampled
Pre-MC ASIFemale Seroincidence Cohort (Cohort A1) – 6 month follow-up period							
2615	1.25	1.09	7106	1.73	12,301	1.21	14884
Post-MC ASIFemale Seroincidence Cohort (Cohort A2) – 12 month follow-up period							
5297	1.25	1.14	7524	1.73	13,023	1.21	15758

With total effective person years of 7912 in the women, assuming a seroincidence rate of 3.0 per 100 person years, and a sample ratio of 1:2, we have 68% power to detect a 30% reduction in HIV seroincidence and 82% power to detect a 35% reduction in HIV seroincidence.

Primary Objective #2a

To estimate HIV incidence rates in the highest risk age subsets of men ages 25-34 in the household-based, nationally representative sample for an additional 6-18 months after the MC ASI completion (Cohort B).

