8.1.4 Analysis of secondary objectives

- 1) To examine the association of baseline demographic characteristics with HIV incidence and prevalence in a household-based representative sample of men and women before and after completion of the MC ASI. Within each cohort, logistic regression will be used to assess association of baseline demographic characteristics with HIV prevalence. Poisson, survival and logistic regression will be used as appropriate to assess associations with seroincidence and baseline demographics. Combined analysis of predictors of seroprevalence and seroincidence using both cohorts will assess effect modifiers associated with cohort (e.g. time) using test for interaction with time. Sample weights will be used in all analyses.
- 2) To determine the prevalence of circumcision among men before and after completion of MC ASI. Population-based circumcision prevalence rates will be computed using appropriate sample weights.
- 3) To estimate HIV prevalence rates among men and women before and after completion of the national male circumcision ASI. Population-based age and gender HIV prevalence rates will be computed using appropriate sample weights.
- 4) To describe sexual risk behavior in a household-based representative sample of men and women before and after completion of the MC ASI. This analysis will be conducted in both HIV-infected and HIV-uninfected participants. Sexual risk behaviors compared between the enrollment pre and post- MC ASI surveys will include the proportion of men and women reporting any unprotected sex and proportion reporting more than one partner. Logistic regression will be used to assess differences in proportions between the baseline cohorts, adjusted for baseline demographic factors, HIV status, and circumcision status (men).

In the two longer longitudinal cohorts of younger HIV-uninfected men (25-34 yrs) and women (18-24 yrs), logistic regression will be used to compare change in behavior from baseline to follow-up. Factors predicting increase and decrease in risk behaviors will be assessed.

- 5) To describe the proportion of HIV-infected men and women in a household-based representative sample of men with undetectable viral loads before and after completion of MC ASI. Logistic regression will be used to assess differences in proportions of male participants with undetectable viral load.

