- 6) To measure the proportion of HIV-infected men and women in a household-based representative sample of men and women who report engagement in HIV care and ART use before and after completion of the MC ASI. Logistic regression

will be used to compare any engagement in care and any ART use in the HIV infected persons identified in the household surveys.

- 7) To describe the CD4 count distribution in a nationally representative sample of HIV-infected men and women ages 18-49. Standard survey sampling approaches using sampling weights will be used to estimate proportions and 95% confidence limits.
- 8) To estimate the proportion of HIV-infected men and women ages 18-49 who have a CD4 count <350 cells/mm³ and who report no current ART use. Standard survey sampling approaches using sampling weights will be used to estimate proportions and 95% confidence limits.
- 9) To describe the viral load distribution in a nationally representative sample of HIV-infected men and women ages 18-49. Standard survey sampling approaches using sampling weights will be used to estimate proportions and 95% confidence limits.

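### Section 8.1.4 item 5 specifies the pre/post viral-load regression for men only, contradicting Secondary Objective 5 and leaving no specified comparison in women

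*Protocol*

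**What the plan says.** Section 3.2, Secondary Objective 5: "To describe the proportion of HIV-infected men and women in a household-based representative sample with undetectable viral loads", before and after the campaign. The Schema has the same objective and lists viral load in infected men and women among the secondary outcomes.

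Section 6.5.1 has both sexes assayed: "Men and women who test HIV-positive via an HIV rapid test during the pre-cohort surveys will have blood specimens tested for viral load". Section 6.7.2 agrees.

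Section 4.2 sets out the intended contrast with no limit by sex: "The proportion of undetectable viral load at the baseline pre-cohort survey will be compared to the post-MC ASI pre-cohort survey". Section 4.0 likewise says that viral load level among those infected at the two surveys will be compared.

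Section 8.1.4 item 5 restates the objective as "To describe the proportion of HIV-infected men and women in a household-based representative sample of men with undetectable viral loads", and then gives the method: "Logistic regression will be used to assess differences in proportions of male participants with undetectable viral load".

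Item 6 of the same section, on care and ART use, states that logistic regression "will be used to compare any engagement in care and any ART use in the HIV infected persons identified in the household surveys". It has no sex restriction.

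**The concern.** The objective, the assays and the design sections cover both sexes, while the one sentence that names an analysis covers men. Followed literally, that sentence leaves the before/after difference in women with no specified comparison. If women are compared anyway, the analysis departs from the written plan.

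The comparison has a purpose. Section 4.2 uses it to explore whether ART scale-up and viral suppression contributed to any fall in incidence, and Section 4.4 lists the undetectable proportion among the data for understanding the effect of expanded care and treatment. Section 2.1 names heterosexual sex as the main driver of the epidemic, and Section 2.3 says that suppression on ART reduces transmission to sex partners. On those premises, suppression among women bears on incidence in men, so a male-only comparison omits a relevant part of the picture.

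**Working it through.** **Text, side by side**

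| Place | Who is covered |
|---|---|
| Schema and 3.2, Secondary Objective 5 | Infected men and women |
| 6.5.1 and 6.7.2, viral-load assays | Both sexes, at the pre-cohort surveys |
| 4.0 and 4.2, pre/post comparison | No sex restriction, no method named |
| 8.1.4 item 5, restated objective | Men and women, but in a sample of men |
| 8.1.4 item 5, method | Male participants |
| 8.1.4 item 6, method | All infected persons |

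Item 6 shows that a restriction to men is not the convention of the section. The protocol gives no corresponding method for women.

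**Scale**

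The protocol states no sample size or power for Secondary Objective 5, so there is no figure to reproduce. The size of the group left out can be derived from Section 7.2.

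Inputs: 12,301 and 13,023 participating households (Tables 2 and 3); 0.92 eligible men and 1.05 eligible women per household; 90% contactable; 95% agreeing to the survey; 99% agreeing to cohort enrolment; 77% of men and 65% of women uninfected, so 23% and 35% infected. For women the protocol writes: "105% will have female residents within the eligible age range, 65% will be HIV uninfected".

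*Route 1, from the stated rates.* Infected participants = households × eligible per household × 0.90 × 0.95 × infected share.

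- Men, first survey: 12,301 × 0.92 × 0.90 × 0.95 × 0.23 ≈ 2,225
- Men, second survey: 13,023 × 0.92 × 0.90 × 0.95 × 0.23 ≈ 2,356
- Women, first survey: 12,301 × 1.05 × 0.90 × 0.95 × 0.35 ≈ 3,865
- Women, second survey: 13,023 × 1.05 × 0.90 × 0.95 × 0.35 ≈ 4,092
- Women's share: 7,957 / (7,957 + 4,581) ≈ 63%

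*Route 2, back from planned enrolment.* Infected participants = enrolled / (0.99 × uninfected share) × infected share.

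- Men: (5,823 + 6,165) / (0.99 × 0.77) × 0.23 ≈ 3,617
- Women: (7,106 + 7,524) / (0.99 × 0.65) × 0.35 ≈ 7,957
- Women's share: 7,957 / (7,957 + 3,617) ≈ 69%

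The routes agree for women and differ for men. The men's enrolled counts rest on the household factor of 2.11 in Table 2, whereas the product printed beside it, 1/(0.92 × 0.77 × 0.99 × 0.90 × 0.95), is about 1.67. Women's enrolment does follow from the stated rates: 12,301 × 1.05 × 0.90 × 0.95 × 0.65 × 0.99 ≈ 7,106. The share is therefore given as a range, 63% to 69%.

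**The case against.** The strongest reply is that the objective is to describe. Item 5 still names men and women, both sexes are assayed at both surveys, Section 7.3 applies sampling weights to all national estimates, and Section 4.2 announces a comparison without restriction. That stands. A reader might infer that Secondary Objective 5 would go unanswered for women; the documents do not support this, because women's proportions can be reported at each survey. What is missing is a specified pre/post comparison for them.

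A second reply is that this is a drafting slip. The garbled restatement of the objective points that way, as does the unrestricted item 6, and a reader should not infer a deliberate decision to exclude women. But a slip in the sentence that fixes the analysis still needs correcting, since an analysis plan covering women would have to depart from the protocol's explicit wording.

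A third reply concerns consequence. A reader might infer that the study loses its main check on ART scale-up as a rival explanation, or that Primary Objective 1a is compromised. Neither follows. Sections 4.3 and 4.4 list several measures side by side, including sexual risk behaviour, ART prevalence and exposure to prevention programmes, and rank none as the main one. Item 6 already compares self-reported care and ART use in all infected persons. Section 4.2 presents the viral-load comparison as exploratory, Sections 2.3 and 7.1 disclaim sole attribution to the campaign, and the incidence rate ratio in Section 8.1.3 does not use the viral-load regression.

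**Conclusion.** The contradiction is real and narrow. Section 8.1.4 item 5 restricts to men a comparison that the objective and the design sections apply to both sexes, and no pre/post comparison in women is specified. The group left out is about 63% to 69% of the expected HIV-infected survey sample. That range assumes the planning rates of Section 7.2 hold, including the infected shares implied by the stated uninfected shares; its width comes only from the two bases for the men's count. Women are the majority on either basis.

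The consequence is a weaker reading of one of several measures for exploring ART scale-up. No primary estimate, test or sample size is affected. The item should be corrected because it is the protocol's only stated method for a named secondary objective.

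**What to change.** In Section 8.1.4 item 5, delete the words that make the sample one of men from the restated objective, so that it matches Section 3.2. In the method sentence, replace male participants with HIV-infected men and women, and state that the proportion with undetectable viral load is compared between the two surveys by sex, using the sampling weights. A combined model with a sex term is optional and can be left to the statistical analysis plan.

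The cost is an edit to two sentences. No assay, visit or sample size changes.

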8.1.5 Multivariate analyses

We will perform multiple regression analyses to examine the independent association of the primary outcome (HIV-incidence) using the covariates identified as significantly associated with the same in bivariate analyses.

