8.1.3 Analysis of primary objectives: Comparison of HIV incidence rates

Primary Objectives 1a & 1b and 2a & 2b

Comparisons of rates of seroincidence in the pre vs post MC ASI will compare incidence rate ratios assuming a Poisson distribution of seroconversions in the follow-up time in each cohort. The HIV seroincidence rates, computed as the total number of seroconversions divided by the total number of person years, adjusted by sampling weights to achieve a population, age, and gender based estimate of seroincidence will be compared in the pre vs post MC ASI in Cohorts A1 and A2. The statistic is the Wald test statistic for the slope of a Poisson regression with a binary covariate for pre vs post MC ASI. Cohorts A1 and A2 are based on independent samples. Each is intended to be representative of the contemporary Swaziland population, thus the sample weighting in each cohort will be based on current population estimates. s

For men in the baseline cohort (Cohort A1) who become circumcised between the time of cohort enrollment and follow-up, only person years prior to circumcision will be included in the analysis. All follow-up time from men who are circumcised prior to enrollment, and men who remain uncircumcised at follow-up, will be included. All follow-up time from women will be included.

To account for potential dependence of HIV seroincidence within households a sensitivity analysis using bootstrap resampling techniques will assess the effect of sampling multiple people from each household on the primary analysis.

Sensitivity analyses will be conducted to assess the impact of any population based demographic changes in the HIV-uninfected population between the pre and post MC ASI periods.

Primary Objective 3

Comparisons of rates of seroincidence in the circumcised vs. uncircumcised men in the post-MC ASI male cohorts will compare incidence rate ratios assuming a Poisson distribution of seroconversions in the follow-up time in each group. The HIV seroincidence rates, computed as the total number of seroconversions divided by the total number of person years in each group, adjusted by the cohort sampling weights to achieve a population age-based estimate of seroincidence will be compared in the circumcised vs. uncircumcised men. The statistic is the Wald test statistic for the slope of a Poisson regression with a binary covariate for circumcision.

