Person years of men who are uncircumcised at the time of cohort enrollment and become circumcised during the 12-month follow-up period will be included in the uncircumcised follow-up until time of circumcision, and in the circumcised follow-up after the time of circumcision.

The exploration of factors that are significant effect modifiers and/or confounders of HIV seroincidence between these two groups will be used to further understand observed differences.

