8.1.6 Controlling for potential confounding variables

For all analyses of the primary outcome, we will control for potential confounding variables by either stratification or including the variable(s) as covariates in the multivariate analyses.

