8.1.7 Alternative comparisons

Identification of a comparable group of uncircumcised men and unaffected women within the accelerated implementation context is challenging. It is acknowledged that men who choose to forego circumcision when it is widely available may differ in important characteristics (both observable and unobservable) from men who undergo MC. The most obvious possibility is that men who have riskier behaviors (and higher HIV risk) may have a greater propensity to seek circumcision than men who practice safer sex. If the decision to be/not be circumcised is correlated with HIV risk, then attempts to properly isolate the impact of MC on HIV may be limited in a simple comparison of men who have undergone and foregone circumcision. Although many measures of sexual risk can be ascertained from all men at baseline and follow-up surveys and controlled for in analyses, there may remain important immeasurable, undetected differences.

Short of randomization, for which equipoise has long since been reached, only second best analytical approaches can be used as a means of controlling for selectivity of

circumcision choice, such as non-experimental matching approaches. Matching estimators typically assume that the decision to undergo MC can be considered to be representative after conditioning on a set of observable characteristics. This approach compares the behavioral outcomes of men undergoing and foregoing MC, after controlling for differences in their observable characteristics. Because the set of observable characteristics is likely to be large, propensity score matching estimators can be used to reduce the matching problem to one dimension. This approach will be explored.

Marginal structural models (MSM) may also be useful in our analyses, as sexual risk behaviors may change over time relative to circumcision. MSM are utilized to mitigate biases introduced by time-dependent covariates for dichotomous outcomes, and aid in causal inference in observational evaluations [Robins, 2000].

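### Protocol 8.1.5 and 8.1.6 give two unreconciled rules for choosing covariates, and the significance screen in 8.1.5 can omit a weak-to-moderate confounder of the circumcision comparison

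*Protocol*

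**What the plan says.** Four parts of the protocol's data analysis plan bear on covariate choice.

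- Section 8.1.5 aims at independent associations with HIV incidence and fills the regression "using the covariates identified as significantly associated with the same in bivariate analyses". It gives no significance threshold and does not name the circumcision contrast.
- Section 8.1.6, for all analyses of the primary outcome, says "we will control for potential confounding variables by either stratification or including the variable(s) as covariates in the multivariate analyses". It has no significance condition, no list of variables and no way of identifying a confounder.
- Section 8.1.3, for Primary Objective 3, fixes the main test: "The statistic is the Wald test statistic for the slope of a Poisson regression with a binary covariate for circumcision". It then adds as a further step "The exploration of factors that are significant effect modifiers and/or confounders of HIV seroincidence between these two groups".
- Section 8.1.7 gives as the most obvious form of self-selection that "men who have riskier behaviors (and higher HIV risk) may have a greater propensity to seek circumcision than men who practice safer sex". It says that "many measures of sexual risk can be ascertained from all men at baseline and follow-up surveys and controlled for in analyses", that "propensity score matching estimators can be used to reduce the matching problem to one dimension" (to be explored), and that "Marginal structural models (MSM) may also be useful in our analyses".

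**The concern.** The goal of 8.1.5 is conditional: does a factor predict incidence once the others are held fixed? Its entry rule is marginal: is the factor significant on its own? The two can part company in the situation that 8.1.7 describes. If riskier men are circumcised more often and circumcision protects, the bivariate risk-behaviour association shrinks. The screen then loses power for the confounder that the protocol itself raises, and a non-significant result is read as a reason not to adjust.

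Section 8.1.6 points the other way, but it speaks of covariates in the multivariate analyses, and 8.1.5 is where entry to those analyses is defined. An analyst could follow either section after seeing the data. The main Objective 3 test has no other covariate, and the propensity-score and marginal structural approaches are only possibilities. The adjusted model therefore carries much of the defence against self-selection.

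**Working it through.** The plan states no figure on this point, so there is none to reproduce. The check asks how often the screen would miss a confounder and what that does to the circumcision rate ratio.

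**Inputs from Protocol 7.2, Primary Objective #3.** 6,165 men less 12% loss gives 6,165 × 0.88 = 5,425 person-years. The rate in uncircumcised men is 2.5 per 100 person-years. The circumcision rate ratio θ is 0.45 (a 55% decrease). Either 80% or two thirds of the men are circumcised.

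**Assumed, not in the protocol.** One binary risk behaviour in a share q of men; uptake p1 in those men and p0 in the others; rate ratio R for the behaviour given circumcision status; a two-sided 0.05 screen; no weights or design effect.

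**Formulas.**
- Marginal rate ratio of the behaviour: M = R × (p1θ + 1 − p1) / (p0θ + 1 − p0).
- Probability that the screen keeps it: about Φ(ln M / SE − 1.96), with SE = √(1/E1 + 1/E0), where E1 and E0 are expected events in men with and without the behaviour.
- Unadjusted circumcision rate ratio: θ × [1 + s1(R − 1)] / [1 + s0(R − 1)], where s1 and s0 are the shares of risk men among circumcised and uncircumcised men.

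**Mild self-selection.** q = 30%, p1 = 87%, p0 = 77%: 80% circumcised, odds ratio (0.87/0.13)/(0.77/0.23) = 2.0. Take R = 2.
- M = 2 × 0.5215/0.5765 = 1.81.
- s1 = 0.261/0.80 = 0.326 and s0 = 0.039/0.20 = 0.195.
- Rate in uncircumcised men without the behaviour: 0.025/1.195 = 0.0209.
- E1 = 35.5, E0 = 45.8, SE = 0.224, ln M/SE = 2.65. Kept: Φ(0.69) = 75%.
- Unadjusted rate ratio: 0.45 × 1.326/1.195 = 0.50.

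**Strong self-selection.** q = 40%, p1 = 85%, p0 = 55%: 67% circumcised, odds ratio (0.85/0.15)/(0.55/0.45) = 4.6. Take R = 2.
- M = 2 × 0.5325/0.6975 = 1.53.
- s1 = 0.34/0.67 = 0.507 and s0 = 0.06/0.33 = 0.182. Base rate: 0.025/1.182 = 0.0212.
- E1 = 48.9, E0 = 48.0, SE = 0.203, ln M/SE = 2.08. Kept: Φ(0.12) = 55%.
- Unadjusted rate ratio: 0.45 × 1.507/1.182 = 0.57.

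Simulating 4,000 cohorts per scenario, and adjusting only when the screen is significant, gives these geometric mean circumcision rate ratios:

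| Uptake odds ratio | R | M | Kept by screen | Unadjusted | Screened | Coverage of 95% CI |
|---|---|---|---|---|---|---|
| 2.0 | 1.5 | 1.36 | 26% | 0.48 | 0.47 | 95% |
| 2.0 | 2 | 1.81 | 75% | 0.50 | 0.46 | 95% |
| 2.0 | 3 | 2.71 | 99% | 0.54 | 0.46 | 95% |
| 4.6 | 1.5 | 1.15 | 10% | 0.52 | 0.51 | 92% |
| 4.6 | 2 | 1.53 | 55% | 0.57 | 0.49 | 91% |
| 4.6 | 3 | 2.29 | 98% | 0.67 | 0.45 | 95% |

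Always adjusting gives 0.45 to 0.46 with about 95% coverage in every row, so the 0.46 at R = 3 is not caused by the screen. With R = 2, the other scenarios with odds ratios of 4 to 7 (92% vs 72%, 95% vs 74%, 90% vs 57%) give 0.48 to 0.50 with 90 to 94% coverage.

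**Masking versus low power.** At R = 2, a test of the behaviour given circumcision detects it about 85% of the time in the mild case (screen 75%) and 88% in the strong case (screen 55%). At R = 1.5 even that conditional test detects it only 41 to 44% of the time, so few events explain much of the loss there.

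**The case against.** The strongest reply is that 8.1.6 already settles the matter. It covers all analyses of the primary outcome, sets no significance condition, and is followed by a section naming sexual risk as measurable and controllable. On that reading sexual risk enters whatever its bivariate p-value. This reading is fair, but the text does not compel it, because neither section refers to the other. It does rule out the stronger inference that the adjusted circumcision effect necessarily stays biased.

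A reader might also infer that the screen tends to drop the very confounder the protocol names. The figures do not support that as a general statement. A moderate confounder is kept about three times in four at an uptake odds ratio near 2, and a strong one almost always. A 0.20 screen, which 8.1.5 does not exclude, would keep the mild R = 2 case about 91 to 92% of the time. Much worse results, such as 26% retention and about 80% coverage, need an odds ratio of 9 and a true rate ratio of 0.40, which is not the Objective 3 input.

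Three further points stand.
- Section 8.1.5 is a general incidence model, and the main Objective 3 test has circumcision as its only covariate, so the screen cannot alter that test.
- Section 8.1.7 says only that riskier men may seek circumcision. If uptake ran the other way, the masking and the direction of bias would reverse.
- The shift is small beside sampling error. With a standard error of the log rate ratio near 0.23, a 95% interval around 0.45 is 0.45 × exp(±1.96 × 0.23), about 0.29 to 0.71.

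The exact covariate list could be left to the SAP. The entry rule, however, is stated in the protocol, so it is a poor stated rule and not missing detail.

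**Conclusion.** The point holds in limited form. The protocol gives two covariate rules without reconciling them, and the one based on bivariate significance is a poor way to choose confounders. If riskier men take up circumcision more often, that rule can omit a weak-to-moderate confounder and move the adjusted rate ratio somewhat toward no protection.

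Against a true 0.45, the screened estimate is about 0.46 to 0.47 at an uptake odds ratio near 2. At odds ratios of 4 to 7 it is about 0.48 to 0.50 for a confounder of rate ratio 2, and about 0.51 in the one case run at rate ratio 1.5. For a strong confounder the effect is negligible. These sizes rest on a single binary confounder with assumed prevalence, strength and uptake gap, and on a 0.05 screen. Sexual risk is in fact several self-reported measures, each of which could fail the screen separately, so their combined effect could be larger than shown. This is a cheap improvement and not a threat to the main Objective 3 test.

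**What to change.** In 8.1.5, state that for circumcised versus uncircumcised men the confounders meant in 8.1.6 enter regardless of bivariate p-value. A suitable set is age group, marital status, employment, region and urban or rural residence, number of partners, and unprotected sex. If events are few (roughly 80 to 100 are expected in the scenarios above), combine them in one propensity score, a tool 8.1.7 already mentions. In 8.1.3, drop *significant* as the criterion for confounders in the Objective 3 follow-on analysis.

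No new data are needed: the pre-cohort survey collects the demographic and behavioural items, and location is known from the sampling. The cost is wording and a few extra degrees of freedom if some covariates prove irrelevant.
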